6.5.1.2 Extended Cardiac Monitoring

Participants who do not meet the discharge criteria at 6 hours postdose will require extended cardiac monitoring, as described below:

- Vital signs will be assessed hourly and 12-lead ECG may be performed, as clinically indicated, until the participant meets the discharge criteria ([Section 6.5.1.1](#)).
- Should a participant require pharmacologic intervention for symptomatic bradycardia, continuous overnight ECG monitoring in a medical facility should be instituted, and the first dose monitoring strategy should be repeated after the second dose of VTX002.
- Should postdose bradycardia (eg, HR < 50 bpm) or potentially related symptoms (eg, dizziness) occur, then initiate appropriate medical management, assess vital signs, begin continuous ECG monitoring, and continue observation until the symptoms have resolved.
- The Medical Monitor should be contacted if the participant does not meet the discharge criteria after ≥ 6 hours of extended cardiac monitoring.
- Any participant who requires extended monitoring on Day 1 (Week 0/Visit 2) or OLE Day 1 (OLE Week 0/OLE Visit 1) must return on the following day for the second dose and will be remonitored as on Day 1 (Week 0/Visit 2) or OLE Day 1 (OLE Week 0/OLE Visit 1), respectively. These participants will be discontinued from study treatment if they do not meet the discharge criteria at 6 hours after the second dose. Extended cardiac monitoring should be continued until the participant meets the discharge criteria ([Section 6.5.1.1](#)).

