6.9 Study Treatment Compliance

The prescribed dosage, timing, and mode of administration may not be changed, except as defined in [Section 6.4.2](#). Any departures from the assigned regimen must be recorded in the eCRFs.

Study treatment compliance will be measured by tablet count. At each visit, prior to dispensing the study treatment, the Investigator will retrieve the previously dispensed study treatment and assess compliance.

Overall, study noncompliance is defined as taking less than 80% or more than 120% of study treatment during the Induction Treatment Period and LTE Treatment Period. Participants will record tablet intake in the eDiary, which will be reviewed periodically by site staff and the Study Team. At each visit, the Investigator will collect the previously dispensed study treatment tablets and assess compliance. If there is a discrepancy between the compliance recorded in the eDiary and the tablet count, it should be discussed with the participant and noted in the source documents.

Participants exhibiting poor compliance should be counseled on the importance of good compliance to the study dosing regimen. Participants who are persistently noncompliant (< 80% or > 120%) should be discussed with the Medical Monitor to determine whether they should be withdrawn from the study.

Details of VTX002 study treatment administration will be documented in the eDiary. The participant will be provided with an eDiary to allow, at minimum, documentation of the date and time of the dose, date(s) of missed doses or partial dose administered while not in the clinic. This information will be transcribed into the participants' eCRF, as appropriate. Participants will be instructed to not take study drug prior to their clinic visits (except for the visits when study drug is not to be administered at the clinic), as predose samples will need to be collected prior to dose administration. While in the clinic, the date/time of doses administered in the clinic will be documented in the eCRF and eDiary. The time and date of study drug administration and the participant's most recent ingestion of food will also be recorded.

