9.4.5 Missing Data

Participants who discontinue treatment will be followed up as participants who do not discontinue treatment, unless consent is withdrawn. A detailed discussion of estimands, intercurrent events, and handling of missing data will be presented in the SAP.

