8. ANALYSIS SETS

The following analysis sets for the Induction Treatment Period are defined as follows:

Full Analysis Set (FAS): The FAS consists of all randomized participants receiving at least 1 dose of study treatment. Under this approach, participants are counted in the treatment group to which they were randomized, regardless of the treatment received during the study.

Modified Full Analysis Set (mFAS): For a given endpoint (see [Section 23](#), Appendix II), mFAS consists of all randomized participants who received at least 1 dose of study treatment and contribute at least one complete endpoint assessment for at least one post-baseline Induction visit. Participants will be analyzed according to the treatment to which they were randomized.

Per Protocol (PP) Set: The PP Set consists of all participants in the primary endpoint mFAS who received $\geq 80\%$ and $\leq 120\%$ of study treatment and do not have a protocol deviation preventing contribution to the primary analysis of the primary efficacy endpoint. Participants experiencing an intercurrent event during the Induction Treatment Period and not experiencing other deviations preventing contribution to the primary and key secondary analyses of the primary and key secondary efficacy endpoints will be included in the PP set and treated as non-responders in these analyses ([Section 3.5](#)).

Safety Set: The Safety Set consists of all randomized participants who received at least 1 dose of study treatment. For this population, participants are analyzed according to the treatment received, regardless of randomization. The Safety Set will be used for all safety analyses in the Induction Treatment Period.

The following analysis sets for the LTE and OLE Treatment Periods are subsets of the analysis sets of the Induction Treatment Period, as defined below:

FAS-Extension Treatment (FAS-ET) Set: The FAS-ET Set consists of all randomized participants who received at least 1 dose of study treatment in the LTE or the OLE Treatment Period. Under this approach, the original treatment groups as assigned at randomization will be used throughout LTE. In general, participants will be analyzed according to protocol-specified intended study treatment dose in FAS-ET analyses. Additional details are provided for specific analyses described elsewhere in this SAP.

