14.2 OTHER MEDICATIONS

Medications not taken for Ulcerative Colitis will be considered prior medications if the end date of the medication is prior to the date of first dose of study treatment. Otherwise, they are considered concomitant medications.

A medication is considered concomitant for the Induction Treatment Period if it meets the following conditions:

- a) Medication started or was ongoing on or after the first study treatment administration date
and
- b) Medication started or was ongoing on or before Visit 7
or
Medication started or was ongoing on or before any of the Early Termination/1-Week Follow-up/2-Week Follow-up visits for participants that permanently discontinue study treatment during the Induction Treatment Period (and are therefore discontinued from the study).

A medication is considered concomitant for the entire study if meets the following conditions:

- c) Medication started or was ongoing on or after the first study treatment administration date
and
- d) Medication study treatment was ongoing on or before the two-week follow-up visit.

Imputation rules specified in Section 10.1 will be applied to partial/missing dates.

Three summaries will be created:

- Prior medications will be summarized by planned treatment group and overall for the FAS, mFAS, and PP sets.
- Concomitant medications taken during the Induction Treatment Period will be summarized by planned treatment group and overall for the Safety, FAS mFAS, and PP sets. This summary will be generated for the Induction Period Analysis.

- Concomitant medications taken during the entire study summaries will be summarized by planned treatment group and overall for FAS ET and PP populations. This summary will be generated at study end.

Additionally, the use of P-gp or BCRP transporters during the study will be flagged in participant-level dataset(s) and in listings. Please see [Section 25](#) (Appendix IV) for WHO Drug Dictionary (WHODD) ATC codes specifying P-gp and BCRP transporters.

If prior medications for UC are inadvertently entered on eCRF pages intended for concomitant medications, these records will be treated as prior medications.

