15.1.2 Tablets Taken, Missed Doses, and Dose Interruptions

The Study treatment Titration (and Study treatment Re-Titration for participants needing it), Study treatment Compliance, Study treatment Overdose, and Study treatment Administration on Site forms will be used to capture drug exposure. Based on these data for the Induction Treatment Period, the following will be calculated:

- Number of tablets taken = total dispensed – total returned
- Number of tablets expected to be taken = number of tablets a participant should have taken between their first and last study treatment administration
- Number of incomplete doses = number of instances where the number of tablets taken in a study day is less than the number tablets the participant should have taken for that study day
- Number of missed doses = number of instances where the participant takes no tablets for a given study day

These will be summarized for the Induction Treatment Period and will also be listed.

The frequency and percentage of participants who had at least 1 dose interruption, who had at least 1 dose interruption of > 7 days, who had at least 1 dose interruption of > 14 days, who had 1

overdose, and who had > 1 overdose will be summarized for the Induction Treatment Period. Interruption is defined as at least one day of missed dose.

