15.2 Compliance

For the Induction Period Analysis, treatment compliance is calculated as (Number of Tablets Taken*100)/(Number of Tablets Expected to be Taken). A participant is non-compliant with study treatment if their treatment compliance is less than 80% or more than 120%. For all bottles not returned, it will be assumed that all dispensed tablets were taken.

This will be summarized by treatment and overall for the Induction Treatment Period. Participant listings will be generated.

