16. EFFICACY

Controlled efficacy analyses are limited to the Induction Treatment Period. Efficacy endpoints may be computed for LTE and OLE study visits, but all hypothesis testing will be uncontrolled, resulting in nominal p-values and CIs only.

The study is designed to show superiority of VTX002 60 mg to placebo for the primary efficacy endpoint at Induction Week 13. Four key secondary endpoints are defined for this study and VTX002 30 mg is an important additional active drug dose of interest. Across the primary endpoint and key secondary endpoints, a total of ten (10) Induction Week 13 controlled hypothesis tests involving the two randomized VTX002 doses and placebo are planned. The family-wise error rate will be maintained at $\alpha = 0.05$ – see [Section 10.3](#) for details.

All controlled efficacy analyses (Week 13, Induction) will be primarily based on participant stratum at randomization (see [Section 10.2](#)) according to IWRS and for the FAS. Participants having MMS = 4 at baseline will be excluded from all efficacy analyses except the sensitivity analysis described in [Section 16.1.5](#). Additional sensitivity and/or supportive analyses will be performed as described elsewhere in this section. For composite scores such as MMS, if one or more components is missing from an analysis visit window the composite score is missing.

Blinded study team review will be used prior to Induction interim database lock and unblinding, to attribute a known Induction Week 13 non-response to participants having specific on-study experiences. Participants will be classified as non-responders in all responder-based efficacy analyses, including the primary endpoint, at all timepoints subsequent to the experience of the earliest of any of the following intercurrent events:

- Missed Visit 7 Week 13 endoscopy for participants eligible to have Visit 7 Week 13 endoscopy
- Discontinuation of the study during the Induction Treatment Period for either disease worsening or treatment-emergent adverse event having a preferred term indicating ulcerative colitis (UC)

- Exposure to rescue therapy for UC. See Appendix IV, [Section 25](#).

For a given participant, if efficacy outcomes (as opposed to components of outcomes) are available subsequent to an intercurrent event, they will be flagged as such. Participants may be included in the PP Set as long as other Per Protocol criteria are not violated.

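### The Per Protocol 80% rule names no period, and the SAP's only compliance formula ends at the participant's own last dose, so it cannot detect a permanent early stop

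*SAP*

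**What the plan says.** **Membership.** SAP Section 8: "The PP Set consists of all participants in the primary endpoint mFAS who received" at least 80% and at most 120% of study treatment, and who have no deviation that keeps them out of the primary analysis. No period is attached to the percentages. The Per Protocol set in Protocol 9.3 has no compliance limit, so the SAP added this one.

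**Formula.** SAP 15.1.2 takes expected tablets as the "number of tablets a participant should have taken between their first and last study treatment administration". Tablets taken are those dispensed minus those returned. SAP 15.2 divides the second by the first and applies the 80% and 120% limits. SAP 15.1.1 takes the last-dose date from the End of Induction form. No other formula appears in the SAP.

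**Period.** Protocol 6.9 defines noncompliance as taking "less than 80% or more than 120% of study treatment during the Induction Treatment Period and LTE Treatment Period". SAP 4.3 repeats the limits over the whole treatment period. Neither gives a formula.

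**After stopping.** Protocol 9.4.5: "Participants who discontinue treatment will be followed up as participants who do not discontinue treatment, unless consent is withdrawn". SAP 14.2 instead refers to participants who "permanently discontinue study treatment during the Induction Treatment Period (and are therefore discontinued from the study". SAP 4.1.5 likewise sends treatment stoppers to an Early Termination (ET) visit and follow-up at 1 and 2 weeks.

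**Intercurrent events.** SAP Section 16 lists "Discontinuation of the study during the Induction Treatment Period for either disease worsening or treatment-emergent adverse event" with a preferred term indicating UC, a missed Week 13 endoscopy, and rescue therapy. A treatment stop for another reason is not on the list.

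**The concern.** The 80% floor is there to keep the Per Protocol set to participants who had most of the planned drug. With a denominator that ends at the last dose, it removes participants with gaps in dosing but not those who stopped for good. SAP 4.3 and Protocol 6.9 point to one denominator and SAP 15.1.2 computes another, so two programmers could build different sets from Section 8.

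The Per Protocol analysis is planned for the primary endpoint and all four key secondary endpoints, at both doses (SAP 16.1.6 and Table 6). If early stoppers with observed Week 13 results stay in, and are more frequent on VTX002, they pull the Per Protocol difference toward zero. If the denominator is settled only after unblinding, its choice is open to influence from the results.

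**Working it through.** **Plan figures used.** The documents give no numerical result for the compliance rule. The sample size supplies the rates and group size used below, and it reproduces: 8% against 28%, two-sided 5%, pooled chi-squared, gives 57 per group with power 0.802; 57 × 1.10 = 62.7, rounded to 63.

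**Step 1: score under SAP 15.1.2.** Take a participant with full adherence up to last-dose day L who returns all unused tablets. Taken equals expected, so compliance is 100% for every L.

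**Step 2: share of planned treatment.** With 91 Induction dosing days, the share is L/91.
- L = 62: 62/91 = 68.1%
- L = 72: 72/91 = 79.1%
- L = 73: 73/91 = 80.2%

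So a last dose on Day 72 or earlier is below 80% of plan. Counting tablets gives nearly the same answer. There are 4 a day from Day 8 (84 × 4 = 336). The titration count is not stated, so I assume 7 to 28 tablets over Days 1 to 7. The share is then 66.2% to 68.1% at Day 62 and 77.8% to 79.1% at Day 72, and 80% is first reached on Day 73 or 74. If 92 days are planned, that becomes Day 74 or 75.

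**Step 3: who can be in the set.** The primary-endpoint mFAS needs ES, RB and SF at one visit (SAP Appendix II, Table 9). The endoscopy must fall on Day 76 to 108, and an ET endoscopy in that window maps to Visit 7 (SAP 9.6, Table 3). RB and SF must be calculable from the eDiary (SAP 10.3).
- *Stoppers leave the study (SAP 14.2, 4.1.5).* Protocol Table 1 schedules an endoscopy at ET and regards an ET visit 2 weeks or more after the last dose as unlikely. With a gap of at most 14 days, the earliest last dose that still reaches the window is Day 76 − 14 = Day 62. The affected range is therefore about Day 62 to 72.
- *Stoppers are followed (Protocol 9.4.5).* A Week 13 endoscopy can exist after a stop at any time, so the range has no such lower end.

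**Step 4: the 100% score is conditional.** Unreturned tablets count as taken. With 2.5 titration tablets a day assumed, a stop on Day 45 with supply to Day 56 kept scores (17.5 + 49 × 4)/(17.5 + 38 × 4) = 213.5/169.5 = 126%, and the upper limit excludes the participant. Inclusion can then turn on whether blister cards came back.

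**Step 5: illustrative effect.** Let m of 63 on 60 mg be retained early stoppers with remission rate r, with none on placebo. The difference is ((63 − m) × 0.28 + m × r)/63 − 0.08.

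| m | r = 8% | r = 0% |
|---|---|---|
| 0 | 20.0 points | 20.0 points |
| 1 | 19.7 | 19.6 |
| 3 | 19.0 | 18.7 |
| 6 | 18.1 | 17.3 |

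The documents give no frequency for m. The value 6 is the full dropout allowance (63 − 57).

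**The case against.** **The period is already stated.** SAP 4.3 states the limits over the whole treatment period. Section 8 speaks of treatment received and does not refer to 15.2, so read with 4.3 it already excludes an early stopper. This stands as far as showing that the SAP is not silent on the period. But 4.3 has no formula and Section 8 does not cite it, so the calculation a programmer can carry out is the one in 15.1.2.

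**The route is narrow.** Under SAP 14.2 and 4.1.5 most early stoppers have no endoscopy in the window. This stands, and it is why about Day 62 to 72 is the main range. Protocol 9.4.5 says otherwise, and the conflict is not resolved.

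**Deviation review may catch them.** It may, but a stop that the protocol requires is not a deviation, the SAP does not say such participants will be removed, and the Protocol Deviation Plan is not among the documents.

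**Compliance while on treatment is a legitimate measure**, and a planned-period rule adds post-randomization selection. Both are true. The first is a reason to keep the 15.2 figure for exposure tables, and the second is a cost of the fix.

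**Stronger readings that a reader might infer.** One is that a participant who had only the 3 mg and 7 mg titration doses, "discontinued from study treatment if they do not meet the discharge criteria at 6 hours after the second dose", ends up in the Per Protocol set. Under SAP 4.1.5 that participant finishes at about Day 16 (2 + 14) with no endoscopy in the window. The case arises only if Protocol 9.4.5 follow-up is carried out. Another is that a Week 13 endoscopy is sufficient for membership; it is not (Step 3). A third is that someone who resumed after a long hold would be excluded while an early stopper stays. A 19-day gap also gives 72/91 = 79.1%, but exclusion follows only if withheld tablets count as expected, and 15.1.2 can be read either way.

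**Conclusion.** The point holds as a minor defect. The 80% floor that SAP Section 8 adds cannot detect a permanent early stop under the only formula provided, and that formula does not match the period in SAP 4.3 and Protocol 6.9. A stop for a reason other than worsening or UC is not an intercurrent event, so an observed Week 13 result would be used.

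The conclusion assumes full adherence before the stop, return of unused tablets, complete ES, RB and SF with an endoscopy on Day 76 to 108, and no other excluding deviation. The Step 5 shifts of 0.3 to 2.7 points are illustrations, not estimates. The frequency is assumed. Six is generous, because the dropout allowance covers people expected to lack data. Remission at 8% or 0% is pessimistic for someone with 9 to 10 weeks of drug. The direction also rests on stops being more common on VTX002. The Phase 1 AV-block discontinuations (Protocol 2.2.2.6) make that plausible for cardiac stops but do not establish it for stops around Day 62 to 72.

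The FAS primary analysis, its multiplicity control and the power are unaffected.

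**What to change.** In SAP Section 8, for Per Protocol membership only:
- Define the percentage as tablets taken divided by tablets planned from Day 1 to the Week 13 visit, or to Day 92 if treatment stopped early.
- State that participants with a Section 16 intercurrent event are not excluded by this rule and stay in as non-responders. Without this exception the new denominator would drop participants who stopped for worsening, whom SAP Sections 8 and 11.2 keep.
- State whether tablets withheld in a protocol-directed hold (Protocol 6.4.2, 7.1) count as planned.

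Keep the first-to-last-dose figure in 15.2 for the exposure tables, labeled as compliance while on treatment, and align the period in SAP 4.3.

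The cost is a few sentences before the interim lock. No new data are needed, because dose dates and tablet counts are already collected. The Per Protocol set becomes slightly smaller, with some added post-randomization selection, since tolerability stops may be more common on VTX002.

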15.2 Compliance

For the Induction Period Analysis, treatment compliance is calculated as (Number of Tablets Taken*100)/(Number of Tablets Expected to be Taken). A participant is non-compliant with study treatment if their treatment compliance is less than 80% or more than 120%. For all bottles not returned, it will be assumed that all dispensed tablets were taken.

This will be summarized by treatment and overall for the Induction Treatment Period. Participant listings will be generated.

16. EFFICACY

Controlled efficacy analyses are limited to the Induction Treatment Period. Efficacy endpoints may be computed for LTE and OLE study visits, but all hypothesis testing will be uncontrolled, resulting in nominal p-values and CIs only.

The study is designed to show superiority of VTX002 60 mg to placebo for the primary efficacy endpoint at Induction Week 13. Four key secondary endpoints are defined for this study and VTX002 30 mg is an important additional active drug dose of interest. Across the primary endpoint and key secondary endpoints, a total of ten (10) Induction Week 13 controlled hypothesis tests involving the two randomized VTX002 doses and placebo are planned. The family-wise error rate will be maintained at $\alpha = 0.05$ – see [Section 10.3](#) for details.

All controlled efficacy analyses (Week 13, Induction) will be primarily based on participant stratum at randomization (see [Section 10.2](#)) according to IWRS and for the FAS. Participants having MMS = 4 at baseline will be excluded from all efficacy analyses except the sensitivity analysis described in [Section 16.1.5](#). Additional sensitivity and/or supportive analyses will be performed as described elsewhere in this section. For composite scores such as MMS, if one or more components is missing from an analysis visit window the composite score is missing.

Blinded study team review will be used prior to Induction interim database lock and unblinding, to attribute a known Induction Week 13 non-response to participants having specific on-study experiences. Participants will be classified as non-responders in all responder-based efficacy analyses, including the primary endpoint, at all timepoints subsequent to the experience of the earliest of any of the following intercurrent events:

- Missed Visit 7 Week 13 endoscopy for participants eligible to have Visit 7 Week 13 endoscopy
- Discontinuation of the study during the Induction Treatment Period for either disease worsening or treatment-emergent adverse event having a preferred term indicating ulcerative colitis (UC)

- Exposure to rescue therapy for UC. See Appendix IV, [Section 25](#).

For a given participant, if efficacy outcomes (as opposed to components of outcomes) are available subsequent to an intercurrent event, they will be flagged as such. Participants may be included in the PP Set as long as other Per Protocol criteria are not violated.

Analysis visits will be mapped according to [Section 9.6 Table 3](#) before any missing data imputation is applied.

